The intestinal microbiota has an influence on host health by, for example, acting through direct and indirect effects on the host immune system and inflammatory response [9, 10]. The structural complexity and functional capability of the intestinal microbiota decline with ageing [11-14]. How this occurs and the nature of the relationship between changes in the microbiota, the onset of low-grade inflammation, declining gastrointestinal tract function, and immunosenescence in older people are not well described. The loss of intestinal barrier function in older people which can result in translocation of bacterial endotoxins and whole bacteria into the bloodstream is a plausible link between intestinal dysbiosis and inflammageing, and is consistent with the concept that manipulation of the intestinal microbiota may be of therapeutic benefit in older people [15]. Nutritional approaches may be used to modify the intestinal microbiota [16, 17] and to support the immune system including regulating inflammation [18].

Fibre is considered essential for the gut to work optimally, and dietary fibre intake is an important determinant of the gut microbiota. Hence fibre affects immunity and inflammation. A high fibre diet seems to reduce the risk of chronic diseases such as cardiovascular disease, type 2 diabetes and bowel cancer. In the UK the recommended dietary intake of fibre is 30 g/day. However, many people do not achieve this. The National Diet and Nutrition Survey reports that, on average, UK adults aged 19 to 64 years consume 19.7 g fibre/day (i.e. 66% of the recommended intake), adults over the age of 65 years consume, on average, 18.7 g fibre/day (62% of the recommendation), and women aged 65 years and above consume, on average, 17.6 g fibre/day (59% of recommendation). It is estimated that only 9% of all adults meet the recommended intake for fibre; this is even lower in older adults where it is estimated that only 4% of women over the age of 65 years achieve the recommended 30 g fibre per day. Thus, there is a shortfall in dietary fibre intake amongst adults, including older people, living in the UK. Soluble corn fibre is used in the food industry. It resists digestion and absorption in the human small intestine and passes into the large intestine (colon) where it can be fermented by intestinal bacteria. In contrast to most available fermentable prebiotic fibres which are fermented in the proximal colon, soluble corn fibre is fermented in the distal colon [19]. Human studies have used soluble corn fibre at intakes of 10 to 20 g/day in both adolescents and adults [20-24]. Soluble corn fibre has been shown to modify faecal microbiota in adults [23] and adolescents [20,21], including an increase in bifidobacteria [23,25]. However, the effect of soluble corn fibre on markers of the immune response is not known, although probiotic bifidobacteria themselves [26] and bifidogenic prebiotics [27,28] have been shown to improve markers of the immune response in older people. The effect of soluble corn fibre on markers of immunity and inflammation will be investigated in this study. Older adults are the target population because immune decline, low grade inflammation and intestinal dysbiosis occur with ageing (these may be linked) and interventions to prevent, slow or reverse such age-related changes are of health relevance. The study will use 20 g soluble corn fibre/day since this amount will bridge the gap between the recommended and average intakes of fibre for the older population and may also positively impact health status of this population. The most recent WHO commissioned systematic review and meta-analysis concluded that additional fibre intake beyond the recommended values of 25-29 g may accrue further health benefits [29]. The proposed dose of soluble corn fibre (20 g/day) is unlikely to result in any gastrointestinal discomfort (doses up to 65 g per day have been shown to be tolerable [30]).

2. Objective

The objective of this study is to identify the effects of soluble corn fibre, in the form of PROMITOR® a Tate and Lyle product used in the food industry, on markers of immunity and inflammation and on faecal microbiota in older adults.

3. Study hypotheses

Soluble corn fibre will:

- a) increase markers of innate immunity (phagocytosis of bacteria (E. coli) by neutrophils and monocytes; natural killer cell activity; monocyte responses to LPS);
- b) increase markers of acquired immunity (T cell responses to stimulation);
- c) decrease markers of intestinal inflammation (faecal calprotectin and iFABP);
- d) decrease systemic markers of inflammation (plasma cytokines, chemokines and CRP);
- e) modify faecal microbiota with an increase in bifidobacteria;
- f) modify the urinary metabolome signalling changes in intestinal microbiota;
- g) increase faecal and circulating short chain fatty acids;
- j) will be well (digestively) tolerated by participants.

4. Inclusion and exclusion criteria

Inclusion criteria

- 1. Community dwelling males and females aged 60 years and older
- 2. Body mass index 18.5-30 kg/m²
- 3. Have regular bowel movements
- 4. Willing to adhere to the study protocol
- 5. Able to provide written informed consent

Exclusion criteria

- 1. Living in a care or nursing home
- 2. Diagnosed with diabetes or other metabolic and endocrine disorders
- 3. Presence of active gastrointestinal disease (coeliac disease, Crohn's disease, diagnosed IBD etc.), autoimmune disease, or inflammatory disease (lupus, rheumatoid arthritis, multiple sclerosis)
- 4. Use of prescribed medicine to control inflammation (e.g. non-steroidal anti-inflammatory drugs; NSAIDs) or regular use of over-the-counter NSAIDs
- 5. Use of dietary supplements (will allow a 4-week washout period)
- 6. Use of probiotic drinks or yoghurts (will allow a 4-week washout period)
- 7. Have extreme habitual fibre intake (lower than 10 g per day or higher than 30 g per day) based on a validated fibre screening tool Fruit/Vegetable/Fiber Screener Free Assessment Tools For Individuals Wellness NutritionQuest [31]
- 8. Blood donation in the previous 3 months.
- 9. Participation in any other clinical trial in the previous 3 months

[figure not shown]
5. Study design and participant schedule

This will be a randomised, controlled, parallel trial in healthy adults aged 60 years and over with BMI 18.5 to 30 kg/m². Volunteers will be screened for eligibility to be enrolled into the study according to standard inclusion/exclusion criteria. 72 participants will be recruited into the study.

All procedures involving human participants will be approved by a relevant NHS Research Ethics Committee. This study will be conducted according to the guidelines established in the Declaration of Helsinki. The study will be registered at www-controlled-trials.com.

Participants will be assessed at baseline, take daily supplements for 3 months, then return for further assessment and conclude the study (see Figure 1).

Figure 1. Overview of the study plan and of participant flow through the study

Recruitment

Participants will be sought through poster advertisements; articles in the media (newsletters, newspapers, radio, and university project specific social media pages); posters and email within the University of Southampton and University Hospital Southampton NHS Foundation Trust; and by contacting those on a GDPR compliant database held by the University Hospital Southampton. Individuals who are interested will contact the research team by telephone. They will then be sent the Participant Information Sheet. They will be able to contact the researcher to confirm their interest. If they do not contact the researcher within 7 days, they will be contacted by the researcher to see if they remain interested in the study. Those individuals who indicate interest in the study will answer a small number of questions to ascertain whether they are likely to meet the inclusion/exclusion criteria (screening questionnaire). If so, an appointment will be made for them to attend visit 1 (V1) at the NIHR Clinical Research Facility at Southampton General Hospital.

Visit 1

Participants will attend the NIHR Clinical Research Facility at Southampton General Hospital in the morning (between 8 and 10 am) in the fasted state (no food or drink apart from water from 9 pm the night before). Participants will be given the opportunity to discuss the study and have any questions answered. If they are happy to be enrolled, they will be asked to sign an Informed Consent Form.

At this visit, participant's height and weight will be measured. ~30 mL of blood will be collected into heparinised tubes to provide whole blood and plasma. After blood collection, participants will be given breakfast (orange juice, toast and jam, tea or coffee) and their habitual diet will be assessed using a Food Frequency Questionnaire. They will complete a gastrointestinal tolerance questionnaire and the Bristol stool chart. During the visit they will provide a urine sample if possible; otherwise they will take a urine collection kit away with them to collect their sample at home. Participants will be provided with a kit to collect a faecal sample to be done prior to using any study products (e.g. later that same day as the clinic visit or the next day) and instructions on how to collect and store the sample. Participants will complete a log recording collection of the sample. A courier service will be used to collect faecal samples from participant's homes.

Participants will then be randomised to one of two groups (corn fibre (20 g/day) or placebo (maltodextrin (calorie-matched dose)) and will receive 4 months supply along with a diary to record that they have taken their supplement each day. The supply of study products will last the 12 week intervention with some to spare in case of a delay in returning for V2. The study materials will be provided in sachets to be stirred into cold water or fruit juice and drunk with meals twice per day. Both corn fibre and maltodextrin are tasteless. Blinding, randomisation, and supplement packaging will be completed by individuals independent of the researchers involved in the study. Participants will be randomised stratified by sex to ensure equal numbers of males and females in each treatment group.

Between visits 1 and 2

Participants will consume soluble corn fibre or maltodextrin daily. They will record this in a daily diary.

Participants will be contacted by the researcher at week 4 and week 8 and will be requested to bring unused supplements to their end of study clinic visit (visit 2; week 12). These will be used to assess compliance.

Visit 2

Three months (12 ± 1 weeks) after Visit 1, participants will return to the NIHR Clinical Research Facility at University Hospital Southampton for visit 2 (V2). Again, they will attend in the fasted state. Participants will be weighed and a ~30 mL blood sample collected into heparinised tubes. After blood collection, participants will be given breakfast (orange juice, toast and jam, tea or coffee) and their habitual diet will again be assessed using a Food Frequency Questionnaire. During the visit participant's will provide a urine sample. One again they will complete the gastrointestinal tolerance questionnaire and the Bristol stool chart. During the visit they will provide a urine sample if possible; otherwise they will take a urine collection kit away with them to collect their sample at home. Participants will be provided with a kit to collect a faecal sample to be done as soon as possible after the study visit and instructions on how to collect and store the sample. Participants will complete a log recording collection of the sample. A courier service will be used to collect faecal samples from participant's homes.

Overview of participant involvement:

| | Visit 1 | Between visits 1 and 2 | Visit 2 |
|------------------------------------|---------|------------------------|---------|
| Informed consent | Х | | |
| Height | Х | | |
| Weight | Х | | Х |
| FFQ | Х | | Х |
| GI tolerance Q | Х | | Х |
| Faecal log and Bristol stool chart | X | | X |
| Blood sample | Х | | Х |
| Urine sample | Х | | Х |
| Faecal sample | Х | | Х |
| Sachet use diary | | Daily | |

6. The intervention

Participants will consume 20 g of soluble corn fibre or calorie-matched maltodextrin daily for 3 months. These materials will be supplied by Tate & Lyle as identical sachets to be stirred into cold water or fruit juice and drunk with meals two times per day. Tate & Lyle will be responsible for preparation, labelling and transportation of materials to the site. Study materials will be stored in a locked, limited access room on Level D of the IDS Building (University of Southampton, Southampton General Hospital campus) dedicated to this purpose. The soluble corn fibre will be PROMITOR® Soluble Fibre as used in the food industry. PROMITOR® Soluble Fibre has been shown to be well-tolerated even at high intake levels (40 g/day bolus or to a total of 65 g/day in multiple doses) [30]. The comparator will be MALTOSWEET™ G 120 (Maltodextrin Non-GMO) given at 2 g/day to match the calorie intake of the soluble corn fibre.

7. Summary of product characteristics

Investigational product

- Product name: PROMITOR® Soluble Fibre
- Active compound: 85A powder (PCR-negative)
- Manufactured by: Tate & Lyle
- Sachets packaged by Calleva Ltd
- Sachet: 12 g compound per Sachet (10 g fibre), consumed twice per day.

PROMITOR® Soluble Corn Fibre 85A is a glucose polymer obtained from partially hydrolysed corn starch and contains a mixture of α 1-6, α 1-4, and α 1-2 glucosidic linkages. In appearance it is an agglomerated powder, white and soluble in water.

It complies with US FDA Regulation 21CFR184.1444 - generally recognised as safe.

A sudden increase in dietary fibre may cause mild gastrointestinal disturbances, but these are generally transient and improve with adaptation to the dietary fibre source. PROMITOR® Soluble Fibre has been shown to be well-tolerated even at high intake levels (40 g/day bolus or to a total of 65 g/day in multiple doses) (30).

Placebo product

- Active compound: MALTOSWEET™ G 120 (Maltodextrin Non-GMO)
- Manufactured by: Tate & Lyle
- Sachets produced by Calleva Ltd
- Sachets: 2 g compound per sachet (0 g fibre), composed of: Maltodextrin

The placebo will be an isocaloric match using Maltodextrin (MALTOSWEET™ G 120). It is a white, practically odourless powder which is soluble in water.

MALTOSWEET™ G 120 complies with the requirements of EU Directives and Regulations in force on foods and food ingredients.

8. Labelling and packaging

The label will contain the following information:

University of Southampton Study code – xxxxx

Ingredient manufactured by Tate & Lyle

Participant Randomisation Number/Code

Investigator name

For clinical trial use only

Batch/Lot number

Storage conditions / keep away from children (if applicable)

Product is packaged in an area with other allergens

Directions for use

Emergency Contact Number

Expiry date

Packaging and labelling will be performed by Calleva Ltd. Labelling of individual boxes with participant randomisation number will be performed by an independent to the study personnel at University of Southampton (keeping study personnel blinded).

Each box will contain 225 sachets allowing for 2 sachets per day, for 84 days (12 weeks) and an extra 57-day supply, in case of delay of visit or loss of investigational product.

9. Compliance

Participants will keep a daily diary recording the use of sachets. They will be asked to return all used and unused sachets at visit 2. The diary and the returned unused sachet count will be used to estimate compliance.

Compliance will be calculated as follows:

$$Compliance \,\% = \, \frac{\textit{Number of sachets dispensed} - \textit{number of sachets returned}}{\textit{number of days in intervention period x 2 doses per day}}$$

In the statistical analysis, overall compliance will be considered.

If a participant states that they have not returned all unused sachets (e.g. forgot to return, loss), these details will be recorded. Participants must have consumed between 80 and 120 % of the investigational product, in order to be deemed compliant. Non-compliant participants will be withdrawn from the per-protocol analysis.

10. Variables and analyses

Markers of immunity and inflammation will be measured in blood samples collected at visits 1 and 2. There is no single marker of "immunity" and therefore a range of static and dynamic markers of innate and acquired immune responses should be measured, as recommended by Albers et al. [32]. Neutrophil phagocytosis of E. coli (median fluorescence intensity reflecting the number of bacteria taken up per neutrophil) will be the primary outcome. All other markers are secondary outcomes.

The following will be measured:

- Immune cell phenotypes in blood (T cells, B cells, monocytes, T helper cells, cytotoxic T cells, regulatory T cells, natural killer cells): flow cytometry [real-time measurement]
- A panel of cytokines and chemokines in plasma: multiplex immunoassay [measurement in stored samples]
- C reactive protein in plasma: immunoassay [measurement in stored samples]
- Neutrophil and monocyte phagocytosis of E. coli: flow cytometry [real-time measurement]
- Natural killer cell activity: flow cytometry [real-time measurement]
- T cell response to stimulation with Con A: CD69 expression (activation marker) and immunoregulatory cytokine production: flow cytometry for CD69; multiplex immunoassay

- for cytokines [real-time culture and flow cytometry; cytokine measurement in stored samples]
- Monocyte response to stimulation with LPS: immunoregulatory cytokine production: multiplex immunoassay [real-time culture and cytokine measurement in stored samples]

Other markers to be assessed (all are secondary outcomes)

- Faecal microbiota to be done in collaboration with Catholic University of Louvain, Brussels
- Faecal short chain fatty acids chromatography [stored samples]
- Faecal calprotectin and intestinal fatty acid binding protein immunoassay [stored samples]
- Plasma short chain fatty acids chromatography [stored samples]
- Urinary metabolome NMR [stored samples]
- GI questionnaire score and Bristol Stool Chart score
- Energy and macronutrient intake from FFQ

Samples will be used as follows:

| Sample | Measurement | Analysed by | Reason |
|--------------|--|---|---|
| Blood plasma | Multiple cytokines and chemokines | Luminex | Inflammatory markers |
| Blood plasma | hs-C-reactive protein | ELISA | Inflammatory marker |
| Blood | Multiple immune cell subsets | Flow cytometry | Identifies blood immune cell phenotypes |
| Blood | Phagocytosis of E. coli by neutrophils and monocytes | Commercial kit + flow cytometry | Indicator of ability to kill bacteria |
| Blood | Natural killer cell activity | Commercial kit + flow cytometry | Indicator of ability to kill tumour cells |
| Blood | T cell activation and cytokines | Culture with stimulant + flow cytometry (CD69) or Luminex (cytokines) | Markers of T cell response |
| Blood | Monocyte cytokines | Culture with stimulant + Luminex (cytokines) | Marker of monocyte response |
| Faeces | Microbiota profiling | Metagenomic sequencing | Identify change in gut microbiota |
| Faeces | Short chain fatty acids | Chromatography | Link with change in gut microbiota |
| Blood plasma | Short chain fatty acids | Chromatography | Link with change in gut microbiota |
| Faeces | Calprotectin; iFABP | ELISA | Markers of intestinal inflammation |
| Urine | Metabolome | NMR | Link with change in gut microbiota |

11. Sample size and statistical analysis

Neutrophil phagocytosis of E. coli will be the primary outcome. Wenisch et al. [33] reported that the number of E. coli taken up by neutrophils was lower by 25% in people aged 62 to 83 years compared to those aged 38 to 56 years. This difference is considered to be relevant to age-related susceptibility to bacterial infection. Some studies of probiotics and prebiotics have reported

enhanced phagocytosis including in older people. The sample size of the current study is based on a 20% increase in neutrophil phagocytosis of E. coli, an effect size based upon the prior studies of probiotics and prebiotics. Using in-house data on mean and SD phagocytosis (median fluorescence intensity using a flow cytometry based commercial kit) 27 participants per group are required to give 80% power to detect a 20% increase as significant with a type-1 error of 5%. To account for 25% drop-out 36 participants will be recruited into each group (i.e. 72 participants in total). All other measurements are secondary outcomes.

12. Data handling and statistical analysis

Data will be entered onto password protected Excel files. Changes between visits 1 and 2 for all outcomes will be compared between groups using unpaired tests. The exact tests used will depend upon the distribution of the data. Where data are not normally distributed, they will be log transformed to attempt to achieve a normal distribution. Regression analyses considering variables such as age, sex and BMI will also be conducted. Statistical analysis will be conducted using the current version of SPSS.

13. Study setting

Clinic visits will take place in the NIHR Clinical Research Facility at Southampton General Hospital. This is an MHRA compliant research facility.

Sample processing and storage and laboratory analysis will take place in laboratories within the Faculty of Medicine, University of Southampton [apart from analysis of faecal bacteria which will be conducted at Catholic University of Louvain, Brussels].

All activities will be according to GCP and follow GDPR protocols.

All staff will be fully trained, including in GCP, with training records.

All laboratory processes will follow SOPs.

14. Adverse events

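### The end-of-study stool is collected at an unspecified time after visit 2, once the product has been handed back, so the secondary faecal outcomes may be measured off-product

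*Protocol*

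**What the plan says.** Four statements in the Protocol bear on the final stool.

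- **Section 5, Visit 2:** "Participants will be provided with a kit to collect a faecal sample to be done as soon as possible after the study visit". A collection log and a courier are provided, but no upper limit in hours or days.
- **Section 9, Compliance:** "They will be asked to return all used and unused sachets at visit 2". Section 5 (Between visits 1 and 2) agrees that participants "will be requested to bring unused supplements to their end of study clinic visit (visit 2; week 12").
- **Section 5, study design:** "Participants will be assessed at baseline, take daily supplements for 3 months, then return for further assessment and conclude the study". The overview table likewise shows the sachet diary only between the visits.
- **Section 5, Visit 1:** the baseline stool is tied to product use: "to be done prior to using any study products (e.g. later that same day as the clinic visit or the next day").

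Section 3 includes the hypothesis that the fibre will "modify faecal microbiota with an increase in bifidobacteria", and section 2 names faecal microbiota in the objective. Section 10 lists all faecal measures as secondary outcomes.

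**The concern.** The baseline stool has a defined relation to product use: before the first sachet, with the same or next day given as examples. The final stool has none. A participant who follows the text hands back the product at visit 2, goes home with a kit and produces a sample later.

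Section 1 describes the fibre as acting by reaching the colon and being fermented there. If supply stops before the sample is taken, part of the effect on the stool may already have faded, and the amount may vary between participants. Fading would pull the groups together, and variation in the gap would add noise.

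The outcomes at stake are faecal microbiota, faecal SCFA, calprotectin and iFABP. Hypotheses c and e rest on this sample, as does the faecal part of g. Urine has a smaller version of the same problem, because a participant who cannot give a sample at visit 2 collects it at home afterwards. The samples cannot be retaken once a participant has finished.

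**Working it through.** **1. The plan's own figure.** Section 11 gives 27 evaluable participants per group and 25% drop-out: 27 / (1 − 0.25) = 36 per group, and 2 × 36 = 72 in total. This reproduces exactly. It concerns neutrophil phagocytosis, which is measured in blood. No effect size, SD or power is stated for any faecal outcome.

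**2. Order of events at the end of the study.**

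| Event | Timing | Protocol source |
|---|---|---|
| Last sachet | Between visits 1 and 2, with a meal | Sections 5 and 6 |
| Fasting blood | At visit 2 | Section 5 |
| Sachets returned | At visit 2 | Sections 5 and 9 |
| Stool kit issued | At visit 2 | Section 5 |
| Stool produced | At home afterwards, no limit | Section 5 |

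Nothing tells participants to keep sachets until the stool is passed. Supply is not the obstacle: 225 − (84 × 2) = 57 sachets would remain after 84 fully compliant days, but the text has them returned.

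**3. Minimum gap, if the visit 1 fasting rule also applies at visit 2.** Visit 1 allows only water from 9 pm and has participants attend between 8 and 10 am. With sachets taken at meals, the last one is at least 11 hours before an 8 am attendance. A stool at 8 am the next day would then be at least 11 + 24 = 35 hours after it. There is no stated maximum.

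**4. Illustration of attenuation.** The Protocol gives no fade rate or gut transit time, so both the half-life *h* and the gap *t* are assumptions. Under exponential fade, the share of the effect kept is 0.5^(*t*/*h*), with *t* counted from the point at which the effect starts to fade.

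| Assumed half-life | 1-day gap | 3-day gap |
|---|---|---|
| 1 day | 50% | 12% |
| 3 days | 79% | 50% |
| 7 days | 91% | 74% |
| 14 days | 95% | 86% |

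The range runs from trivial to severe, and the documents do not say where this trial falls.

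**The case against.** The strongest reply is that attenuation is only an inference. The Protocol asks for prompt collection, supplies a courier and a log, and recruits people with regular bowel movements. A stool passed on the day of visit 2 or the day after may largely reflect intake before the visit. That is fair, and it is why the point is put as a possibility. Even so, a request for promptness sets no limit and does not tie the sample to product use.

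Five stronger readings are tempting, and the documents do not support them.

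- **That the effect is diluted.** There is no fade rate, transit time or washout evidence in the text, and SCFA, microbiota and calprotectin need not fade alike. The end of intake at visit 2 is itself implied by the return of sachets, not stated.
- **That power drops to a particular value.** Any such figure would borrow a standardised effect back-solved from the sample size for the blood outcome. It would describe no planned faecal analysis.
- **That a null faecal result could not be told apart from washout.** If the log records date and time, the interval from visit 2 can be recovered and examined. Its fields are not shown.
- **That blood and stool reflect quite different exposure.** The visit 2 blood is also drawn fasted, so it too follows at least an overnight gap. Against a same-day stool the difference may be hours.
- **That all of hypothesis g is affected.** It also covers circulating SCFA, which come from the visit 2 blood.

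The procedure is the same in both arms, so the expected consequence is attenuation and noise, not a spurious difference.

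**Conclusion.** The point holds in a limited form. As written, the plan takes the final stool after the product has been returned and after an open-ended interval, whereas the baseline stool is anchored to product use. The secondary faecal outcomes may therefore be measured off-product, and a true difference could be understated.

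The size cannot be derived. The 50% to 95% kept after one day rests wholly on assumed half-lives of 1 to 14 days and an exponential fade.

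A reader might infer that the trial's main result is threatened. It is not: the primary outcome is measured in blood drawn at visit 2, and neither it nor the sample size is touched. The change is recommended because microbiota is part of the stated objective and the remedy is cheap. It is not essential to the validity of the primary analysis.

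**What to change.** Reconcile the passages on sachet return and stool timing in sections 5 and 9, so that the final stool is tied to the supplement period.

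- Issue the second kit before visit 2, for example at visit 1 or by post after the week 8 contact. Ask for the sample shortly before the visit (a window of 48 hours is one option), using the existing courier.
- Where a participant expects to need the home urine kit, have that sample taken on the morning of visit 2.
- If some stools will still come after the visit, state a maximum interval.
- Enter the date and time of the last sachet and of the sample in the existing log, and use the interval in a sensitivity analysis of the faecal outcomes. The interval arises after randomisation and may itself depend on bowel habit, so it should not enter the main comparison.

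The cost is amended wording, the same kit and courier used earlier, and one more line in the log. The downside is that participants need a reminder before visit 2. The intervention itself does not change.

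### The compliance formula counts every unreturned sachet as consumed, so a fully adherent participant who does not bring the spares back can be dropped from the per-protocol analysis

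*Protocol*

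**What the plan says.** Protocol section 9 gives compliance as a fraction. The numerator is the sachets dispensed minus the "number of sachets returned", and the denominator is the "number of days in intervention period x 2 doses per day". The cut-off follows: "Participants must have consumed between 80 and 120 % of the investigational product, in order to be deemed compliant". Participants who miss it are taken out of the per-protocol analysis.

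The text around the formula adds three things:

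- The sentence just before it names two sources for estimating compliance, the diary and the count of unused sachets handed back.
- On sachets that do not come back it says: "If a participant states that they have not returned all unused sachets (e.g. forgot to return, loss), these details will be recorded". It gives no next step.
- On what to bring back, section 9 says: "They will be asked to return all used and unused sachets at visit 2". Section 5 (between visits 1 and 2) says that participants "will be requested to bring unused supplements to their end of study clinic visit", with no mention of used ones.

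On supply, section 8 says: "Each box will contain 225 sachets allowing for 2 sachets per day, for 84 days (12 weeks) and an extra 57-day supply". Section 5 (Visit 1) says that participants "will receive 4 months supply along with a diary to record that they have taken their supplement each day". Visit 2 falls at 12 weeks, plus or minus one.

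**The concern.** The formula measures consumption by subtraction, so it is right only if every unused sachet comes back. The box deliberately holds many more sachets than the course needs, so every participant, however adherent, should have a sizeable number left over. A sachet forgotten in a cupboard and a sachet taken in excess of two per day add the same amount to the score.

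Section 9 foresees non-return but gives no rule for it. Neither the recorded losses nor the diary changes the calculated percentage or the decision to exclude. Membership of the per-protocol set then depends partly on how completely spares are brought back. If staff correct scores case by case instead, membership depends on a judgement that could be made after outcome data exist.

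**Working it through.** **Inputs.** 225 sachets per box and 2 per day (section 8); 77, 84 or 91 days of intervention (section 5, 12 ± 1 weeks); range 80% to 120% (section 9). I assume that one box is dispensed and that the days are those actually elapsed.

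**The plan's own supply figure.** 84 × 2 = 168 sachets are needed, and 225 − 168 = 57 are spare. At 2 per day, 57 sachets last 28.5 days. A supply for 84 + 57 = 141 days would take 282 sachets. The 57-day figure therefore does not reproduce from 225 sachets, although 57 is the number of spare sachets. The box as a whole lasts 225 / 2 = 112.5 days, which fits the four months in section 5.

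**Fully adherent participant.** Score = (225 − returned) / (2 × days).

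| Days | Doses due and taken | Spares | Score, all spares returned | Score, none returned | Spares missing that suffice for exclusion |
|---|---|---|---|---|---|
| 77 | 154 | 71 | 100% | 225/154 = 146.1% | 31 (185/154 = 120.1%) |
| 84 | 168 | 57 | 100% | 225/168 = 133.9% | 34 (202/168 = 120.2%) |
| 91 | 182 | 43 | 100% | 225/182 = 123.6% | 37 (219/182 = 120.3%) |

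If the denominator were instead fixed at 84 days, the no-return score would be 133.9% whatever the visit date.

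**Half-adherent participant at 84 days.** 84 taken, so 225 − 84 = 141 unused. Score = (84 + missing) / 168.

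- None missing: 84/168 = 50%, excluded.
- 51 missing: 135/168 = 80.4%, passes.
- 117 missing: 201/168 = 119.6%, passes.
- All 141 missing: 225/168 = 133.9%, excluded.

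**Same cases with reported non-returns also subtracted.** Full adherer at 84 days, none returned, 57 reported left at home: (225 − 0 − 57)/168 = 100%. Half adherer, 90 returned, 51 reported lost: (225 − 90 − 51)/168 = 50%. Both are then classified correctly.

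**Check on the denominator.** Dividing by days from first to last dose would be worse. A participant who takes 84 sachets over 42 days and stops would score 84/(2 × 42) = 100%. The protocol's own denominator gives 84/168 = 50%.

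**The case against.** The strongest reply is that section 9 should be read as a whole. It names the diary as a source, records sachets stated as not returned, and words the cut-off in terms of product consumed. A participant with a complete diary who reports leaving 57 sachets at home is documented as having taken 168, and a sensible team would not exclude that person. Reconciling diary and count could also be left to a statistical analysis plan. What stands is that the information needed for a correction is collected. What does not stand is that the correction is specified: the protocol itself fixes the formula, the range and the consequence, and says nowhere that the other sources alter the result.

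The reply also limits the point, and these limits hold. Participants are contacted at weeks 4 and 8 and asked to bring unused product back, and a full adherer fails at 12 weeks only if most of the spares are missing.

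Three stronger readings are tempting but unsupported:

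- A reader might infer that returning used and unused sachets together gives 0%. The sentence before the formula makes clear that unused sachets are counted, so this is loose labelling only.
- A reader might infer that half-adherent participants commonly pass. They do so only within the band of partial non-return shown above, and their diary would contradict the score.
- A reader might infer a loss of power for the primary result, given 27 needed per group. Section 12 does not make the per-protocol set the primary analysis set, and section 11 does not tie the 27 to it.

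**Conclusion.** The point holds. As written, the rule excludes a participant with perfect intake who returns no spares, at every visit date in the permitted window (124% to 146% against a ceiling of 120%). The result rests on one 225-sachet box per participant and on applying the formula literally. If 282 sachets were really supplied, the no-return scores would rise to 282/182 = 154.9% through 282/154 = 183.1%.

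The consequence is confined to the per-protocol set. The protocol gives no non-return rate, so the number misclassified cannot be estimated. Wrongly dropped adherers cost precision and wrongly kept non-adherers dilute the effect, but nothing in the document shows which would prevail or that the arms would differ. The 57-day statement is a minor inconsistency of units that enters neither the formula nor the cut-off. This should be corrected before the analysis sets are fixed, but it does not threaten the trial's main comparison.

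**What to change.** In section 9:

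- Keep the denominator as twice the days in the intervention period. Do not replace it with days from first to last dose.
- Define the numerator as dispensed, minus unused sachets returned, minus unused sachets reported as lost or not returned, and label the returned term as unused.
- State in advance that where these counts leave sachets unaccounted for, the daily diary count is used to classify compliance.

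In section 8, reconcile the stated extra supply with the box content (57 spare sachets are 28.5 days at 2 per day). Align sections 5 and 9 on whether used sachets are to be brought back.

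The cost is a few sentences of rewording. The diary, the return count and the record of non-returns are already collected. The downside is some reliance on self-report, for the reported losses and for the diary where the counts do not close.
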